according to the following inclusion criteria: patients aged from 45-75 years and had been completely edentulous for a minimum period of 1-year, normal maxillary-mandibular relationship, healthy mucosa, and normal salivary flow. While the exclusion criteria were: smoker patients or patients having hard or soft tissue pathology, severe ridge undercut, and patients who had received radiation to the head and neck region.

This study divided into 2 groups according to type of denture received by the patients:

Group I: Patients received maxillary and mandibular rapid prototype complete denture

- Retention was measured at time of insertion and after 3 week and after 6 week using the retention force gauge device

Group II: Patients received mandibular complete denture constructed from polyamide reinforced with metal frame work and maxillary dentures constructed from conventional Poly-Methyl Methacrylate

- Retention was measured at time of insertion and after 3 week and after 6 week using the retention force gauge device

Sample Size Calculation:

A total sample size of 12 will be sufficient with the power of 80% and 5% significance level. This number will be increased to 20 (10 in each of the two groups) to compensate for follow-up losses. The sample size was determined through the application of the G Power program.

Construction of the 3D model:

For rapid prototype complete denture base, Preliminary impressions was made using irreversible Hydrocolloid Alginate (Cavex Holland BV) then definitive impression and recorded horizontal relationship were done in one visit and sent to a digital laboratory for scanning and 3D printing of the CDs.

The master casts were digitalized using and extraoral 3D scanner * , at which the cast holder used to fix the cast in place,

The digital image (STL file) were imported to Exocad* digital design software to oriented the cast according to proposed insertion and removal pathway and to draw extension of denture base at the depth of vestibules and make design of denture base.

Printing step: the designed denture base were export as STL file and sent to 3D printer software, the denture base were printed according to Digital Light projection (DLP) technology * using Next Dent Baes Liquid* which is a monomer based on acrylic ester. Then the denture base were finished and polished except area at crest of the ridge.

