The measuring device used to measure retention is Digital force gauge *(is an advanced type of force meter device used to Measure Tension or Compression force.

After determining the geometric center for mandibular denture, then mark a point on the plaster base.

Three “V” shaped grooves were created on the polished surface of the lower denture. (Two grooves were created at the retromolar pad area just distal to the second molar of both sides. The other one was made on the lingual flange at the midline region below the central incisors)

A wrought wire of 1 mm in diameter was then bent at its center and adjusted so as not to encroach on the tongue space and to run 2 cm above the occlusal plane from the retromolar pad groove of one side to the retromolar pad groove of the other side.

* Digital Force Gauge EXTECH 475044.

Then free ends of the three wires were then fixed to the polished surface of the lower denture by self-cured acrylic resin.

Retention of mandibular dentures was assessed as follows:

After denture insertion, The metallic probe of the digital force-meter was then attached to the c-shaped metal hook created at the geometric center of the mandibular dentures and a vertical pulling force was applied to measure denture retention. Retention strength was measured in newtons.

Statistical analysis:

All data were presented as mean & standard deviation. Data were presented 1 table & 1 graph. Statistical analysis was performed with SPSS 16 ® (Statistical Package for Scientific Studies), Graph pad prism & windows excel

Exploration of the given data was performed using Shapiro-Wilk test and Kolmogorov-Smirnov test for normality which revealed that the significant level (P-value) was insignificant as P-value > 0.05 which indicated that all data originated from normal distribution (parametric data) resembling normal Bell curve.

Accordingly, comparison between different groups was performed by using Independent t-test, while comparison between different intervals was performed by using One Way ANOVA test followed by Tukey's Post Hoc test for multiple comparisons.

Effect of time (table 1 and figure 1):

In group I, there was a significant difference between all intervals as $P<0.05$, at delivery was significantly the lowest retention (10.58 ± 0.31), while there was

insignificant difference between after 3 months (11.92 ± 0.56) and after 6 months (12.17 ± 0.49) with 15.9% percent of increase in retention for 6 months.

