In group II, there was a significant difference between all intervals as $P<0.05$, at delivery was significantly the lowest retention (16.54 ± 0.52), then after 3 months (18.49 ± 0.58), while after 6 months (19.87 ± 0.59) was significantly the highest with 20.00% percent of increase in retention for 6 months.

Effect of different construction techniques (table 2 and figure 2):

Comparison between group I & II revealed that group II was significantly higher than group I at all intervals as $P <0.05$

Table (1): Mean and standard deviation of retention in both groups and comparison between different intervals with percent of change in each group:

	Follow up	M	SD	% change	P value
Group I (3D printed denture)	At delivery	10.58 ^a	0.31	15.90%	<0.0001*
	After 3 weeks	11.92 ^b	0.56		
	After 6 weeks	12.17 ^b	0.49		
Group II (metal reinforced denture)	At delivery	16.54 ^a	0.52	20.00%	<0.0001*
	After 3 weeks	18.49 ^b	0.58		
	After 6 weeks	19.87 ^c	0.59		

M: mean

SD: standard deviation

*Significant difference at $P <0.05$

Means with different superscript letters were significantly different as $P <0.05$

Means with the same superscript letters were insignificantly different as $P >0.05$

[figure not shown]

Figure (1): line chart representing retention changes of both groups during different intervals.

Table (2): Comparison between group I & II regarding retention at different intervals using Independent t-test:

Interval	N	Group I		Group II		Independent t-test			
						P value	MD \pm SEM	95% CI	
		M	SD	M	SD			L	U
At time delivery	7	10.58	0.31	16.54	0.52	0.0001 *	5.9 \pm 0.2	5.4	6.4
After 3 weeks	7	11.92	0.56	18.49	0.58	0.0001 *	6.6 \pm 0.3	5.9	7.2
After 6 weeks	7	13.24	0.49	19.87	0.5	0.0001 *	6.63 \pm 0.3	6.05	7.21

M: mean SD: standard deviation *Significant difference at $P < 0.05$

Difference between means ($B - A$) \pm standard error of mean

CI: confidence intervals at 95% (U: upper / L: lower)

[figure not shown]

Figure (2): Bar chart representing retention in both groups.

REFERENCES

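### Group I's 6-week mean is 12.17 N in the text and Table 1 but 13.24 N in Table 2, so the final group difference (7.70 or 6.63 N) and Group I's course after 3 weeks are undetermined

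*Combined protocol and SAP*

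**What the plan says.** Retention, in newtons, is the only outcome. Materials and Methods sets the same three visits for each group: "Retention was measured at time of insertion and after 3 week and after 6 week using the retention force gauge device".

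The last visit is reported in three places:

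- **Statistical analysis, Effect of time (text).** For Group I the text finds no significant difference between the second visit (11.92 ± 0.56) and the last, which it reports as "after 6 months (12.17 ± 0.49) with 15.9% percent of increase in retention for 6 months". The same sentence opens "In group I, there was a significant difference between all intervals". For Group II the text says "while after 6 months (19.87 ± 0.59) was significantly the highest".
- **Table 1.** The Group I row is "After 6 weeks 12.17 ^b 0.49". The letter b is shared with the 3-week mean of 11.92, and the footnote defines a shared letter as not significantly different. The Group II SD is 0.59.
- **Table 2.** The 6-week row gives the Group I mean and SD, then those of Group II, as "13.24 0.49 19.87 0.5". The difference is 6.63 ± 0.3 N, 95% CI 6.05 to 7.21, with N shown as 7.

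The text dates the follow-up visits in months, whereas the Methods and both tables use weeks. The between-group conclusion is that "group II was significantly higher than group I at all intervals".

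**The concern.** One group at one visit has two means, 1.07 N apart, with the same SD of 0.49. The Group I means at delivery (10.58) and 3 weeks (11.92) agree across the tables, so the conflict is confined to the last visit. If 13.24 were a stray misprint, the rest of Table 2's row should follow from 12.17. If 12.17 were the misprint, Table 1's letters should follow from 13.24. If neither happens, the document holds two incompatible analyses of the final visit, and readers of the two tables would take away different effect sizes and different time courses.

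Three further items in the same lines need checking: the 15.9% gain, the Group II SD (0.59 or 0.5), and the opening statement that all Group I intervals differ, which reads as contradicting the pairwise result after it.

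**Working it through.** **Inputs** (mean ± SD, N, from the text and Tables 1 and 2)

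- Group I: delivery 10.58 ± 0.31; 3 weeks 11.92 ± 0.56; 6 weeks 12.17 or 13.24, SD 0.49.
- Group II: delivery 16.54 ± 0.52; 3 weeks 18.49 ± 0.58; 6 weeks 19.87, SD 0.59 or 0.50.
- n = 7 per group. This is an assumption, because Table 2 does not say whether its N is per group. It is tested in step 1.

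**Step 1. Reproduce Table 2.** Difference = M2 − M1; SE = √[(SD1² + SD2²)/7]; 95% CI = difference ± 2.179 × SE (t with 12 df).

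| Visit | Recomputed | Printed |
|---|---|---|
| Delivery | 5.96 (5.46 to 6.46) | 5.9 (5.4 to 6.4) |
| 3 weeks | 6.57 (5.91 to 7.23) | 6.6 (5.9 to 7.2) |
| 6 weeks, using 13.24 and SD 0.50 | 6.63 (6.05 to 7.21) | 6.63 (6.05 to 7.21) |

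At 6 weeks, SE = √[(0.49² + 0.50²)/7] = 0.265. The 3- and 6-week rows match on ordinary rounding. The delivery row matches only if its decimals were truncated. With 10 per group the intervals are too narrow (3 weeks: 6.03 to 7.11), so 7 per group is the reading that fits. The mean of 13.24 was therefore used to compute Table 2's difference and interval.

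**Step 2. All four combinations at 6 weeks**

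| Group I mean | Group II SD | SE | Difference (95% CI), N | p |
|---|---|---|---|---|
| 13.24 | 0.50 | 0.265 | 6.63 (6.05 to 7.21) | 9.9e-12 |
| 13.24 | 0.59 | 0.290 | 6.63 (6.00 to 7.26) | 2.9e-11 |
| 12.17 | 0.59 | 0.290 | 7.70 (7.07 to 8.33) | 5.0e-12 |
| 12.17 | 0.50 | 0.265 | 7.70 (7.12 to 8.28) | 1.7e-12 |

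The shift is 7.70 − 6.63 = 1.07 N, and 1.07/6.63 is about 16%. The value 7.70 lies outside the printed interval. The choice of SD moves each limit by only about 0.05 N. As ratios, 19.87/13.24 = 1.50 and 19.87/12.17 = 1.63.

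**Step 3. Group I, 3 to 6 weeks, by the stated method** (one-way ANOVA with Tukey, n = 7 at each visit, 18 df). MSE = (0.31² + 0.56² + 0.49²)/3 = 0.2166. The standard error for q is √(0.2166/7) = 0.176, and the 5% threshold for a pairwise difference is 0.635 N.

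- With 12.17: change 0.25 N, q = 1.42, p = 0.58. This fits the shared letter b.
- With 13.24: change 1.32 N, q = 7.50, p = 0.00014. This would need a different letter.

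The result flips in the same way at n = 6 (p = 0.63 and 0.0005) and n = 10 (p = 0.46 and 0.000003).

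**Step 4. Percent gain from delivery**

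- Group I: 12.17/10.58 − 1 = 15.0%, or 13.24/10.58 − 1 = 25.1%.
- Group II: 19.87/16.54 − 1 = 20.1% (printed 20.00%).

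The printed 15.9% equals neither Group I figure and would need a mean of about 12.26. Rounding of the means allows only 14.9% to 15.1% from 12.17. Averaging individual percent changes does not explain it either: simulated from the printed means and SDs, with within-patient correlations from −0.9 to 0.9, it gives 15.0% to 15.3% with 12.17. The absolute gain is 12.17 − 10.58 = 1.59 N, so 15.9% may be a separate slip. The documents do not say how the percentage was computed.

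**The case against.** The strongest reply is that the documents lean towards 12.17. It is printed twice, it fits the letters and the text, and its gain of 1.59 N shares its digits with the printed 15.9%. The 13.24 row stands alone and reports its difference to two decimals where the other rows use one, so it may have been computed separately from a mistyped mean. Agreement within that row would survive such an error. This is reasonable inference, but it proves nothing about the readings. If it is right, Table 2's final difference and interval are wrong.

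A second reply is that the study's answer is untouched: Group II is higher at every visit, the documents name no primary time point, the conclusion is blank, and nowhere are the groups ranked on relative gain. The first part stands. The fault concerns the size of the final difference and one within-group comparison, and the relative-gain ranking is a consequence for readers, not a claim of the authors.

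Third, the Tukey check treats repeated visits as independent. It follows the documents' own method, so it tests the printed letters fairly, but it does not establish a plateau. In an unadjusted paired test at n = 7, a change of 0.25 N gives p = 0.26 at an assumed within-patient correlation of 0.5, 0.10 at 0.8 and about 0.035 at 0.9.

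Finally, the Group II SD and the statement about all intervals are minor. The latter may simply report the overall ANOVA. Neither would call for action alone.

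**Conclusion.** The concern holds. Two means are printed for Group I at the last visit of the only outcome, each supports its own set of results, and only the source readings can settle which is right.

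What depends on the choice:

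- The final difference is 6.63 N (6.05 to 7.21) or 7.70 N (7.07 to 8.33), putting Group II 50% or 63% above Group I.
- Group I's change from 3 to 6 weeks is 0.25 N, not significant, or 1.32 N, clearly significant, under the stated method.
- Group I's gain from delivery is below Group II's (15.0% against 20.1%) or above it (25.1%).

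What does not depend on it is the direction and significance of the group comparison, with p between 1.7e-12 and 2.9e-11 across all four combinations.

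The two point differences need no assumption. The intervals and p-values assume 7 patients per group, and the Tukey results also follow the documents' treatment of the visits as independent. This must be corrected before any 6-week result is quoted.

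**What to change.** 1. Go back to the patient-level 6-week readings and establish the Group I mean and the Group II SD.
2. Regenerate Tables 1 and 2, the post hoc letters, the percent changes and Figures 1 and 2 from one locked dataset. State how the percentages are computed and use one rounding rule throughout Table 2. The figures were not available for this check, so which mean they plot is unknown.
3. In the Group I text, give the overall ANOVA result and the pairwise results in separate sentences.
4. Reconcile months in the results text with weeks in the Methods and tables.
5. State in Table 2 whether N is per group.

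The cost is a check of one visit's readings (14 patients if N = 7 is per group), a rerun of two tables and two figures, and some rewording. No new patients or procedures are involved.

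### The Group I percent increase in retention (15.9%) fits neither of the two last-visit means printed for that group: one gives 15.0%, the other 25.1%

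*Combined protocol and SAP*

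**What the plan says.** In the results under Effect of time, the Group I figures are a delivery value described as "at delivery was significantly the lowest retention (10.58 ± 0.31") and a last-visit value of 12.17 N (SD 0.49), reported "with 15.9% percent of increase in retention for 6 months". Table 1 carries the same means, 10.58 and 12.17 N, and prints the change as 15.90%. Its title announces a "comparison between different intervals with percent of change in each group".

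For Group II the text starts from 16.54 N at delivery and ends "after 6 months (19.87 ± 0.59) was significantly the highest with 20.00% percent of increase in retention for 6 months". Table 1 also prints 20.00%.

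Table 2, which compares the groups at each visit with n = 7, gives the Group I last-visit mean as 13.24 N, not 12.17 N.

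No formula for percent change is stated. No mean change with a standard deviation or confidence interval is reported for either group. The text labels the follow-up visits in months where the methods and tables say weeks, so the final reading is called the last visit here.

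**The concern.** A percent change printed next to the means it summarises should be recoverable from them. For Group I it is not. The visit means, ANOVA P values and Tukey letters also describe change over time, but the percentage is the only figure that puts a size on the change within each group, and it appears in both the text and Table 1.

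A reader who sets the two groups side by side reads 15.9% against 20.00%, with Group II ahead by 4.1 percentage points. If that ordering or gap is quoted, it rests on a number that neither printed mean supports.

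**Working it through.** **Inputs**

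- Group I delivery: 10.58 N, SD 0.31 (text, Tables 1 and 2).
- Group I last visit: 12.17 N, SD 0.49 (text, Table 1); 13.24 N, SD 0.49 (Table 2).
- Group II delivery and last visit: 16.54 and 19.87 N (text, Tables 1 and 2).
- n = 7 (Table 2).

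**1. Attempt to reproduce 15.9%**

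Percent change = 100 × (last mean − delivery mean) / delivery mean.

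- With 12.17 N: 1.59 / 10.58 = 15.03%. Moving both means to their rounding limits gives 1.58 / 10.585 = 14.93% to 1.60 / 10.575 = 15.13%.
- With 13.24 N: 2.66 / 10.58 = 25.14%.

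Neither gives 15.9%. That figure would need a last-visit mean of 10.58 × 1.159 = 12.26 N, or a delivery mean of 12.17 / 1.159 = 10.50 N. Neither value is printed.

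**2. Other definitions, using 12.17 N**

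- Last mean as denominator: 1.59 / 12.17 = 13.06%.
- Midpoint as denominator: 1.59 / 11.375 = 13.98%.
- Log ratio: ln(12.17 / 10.58) = 14.00%.
- Sum of the two steps through 11.92 N: 12.67% + 2.10% = 14.76% (from unrounded steps).

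With 13.24 N, the last mean as denominator gives 2.66 / 13.24 = 20.09%.

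**3. Mean of per-patient percentages**

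This can differ from the change in means. To second order, the mean ratio is (m₂/m₁) × [1 + ((n−1)/n) × (c₁² − r·c₁·c₂)], where c₁ and c₂ are the coefficients of variation and r is the correlation between visits. It is largest at r = −1. With c₁ = 0.31/10.58 = 0.0293, c₂ = 0.49/12.17 = 0.0403 and n = 7, the bracket is 1 + (6/7)(0.00086 + 0.00118) = 1.00175, and 1.1503 × 1.00175 = 1.1523, or about 15.2%. Direct numerical maximisation gives 15.24% at n = 7, 15.26% at n = 10, and 15.35% at n = 7 with means and SDs at their rounding limits. So 15.9% is out of reach on Table 1's figures.

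**4. Group II by the same formula**

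3.33 / 16.54 = 20.13%, with rounding limits 20.07% to 20.20%. The printed 20.00% is right to the nearest whole percent, but its two decimals are not supported.

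**5. What each last-visit mean implies**

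| Group I last visit | Gain | Percent | Against Group II (20.13%) |
|---|---|---|---|
| 12.17 N | 1.59 N | 15.03% | Group I lower by 5.10 points |
| 13.24 N | 2.66 N | 25.14% | Group I higher by 5.01 points |

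**6. Do the documents settle which mean is right?**

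- Table 2's last row prints a difference of 6.63 (6.05 to 7.21). With 13.24 N: 19.87 − 13.24 = 6.63; SE = √((0.49² + 0.50²)/7) = 0.265; with t(12) = 2.179 the interval is 6.05 to 7.21. This matches. With 12.17 N the difference would be 7.70.
- Table 1 gives the two follow-up visits of Group I the same letter, meaning no significant difference. Pooled variance = (0.31² + 0.56² + 0.49²)/3 = 0.2166; SE = √(0.2166/7) = 0.176. With 12.17 N, q = 0.25/0.176 = 1.42 and Tukey P is about 0.58, which agrees with the letter. With 13.24 N, q = 1.32/0.176 = 7.50 and P is about 0.0001, which does not.

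Each table is consistent with its own mean, so the documents do not decide between them.

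**7. Table 2, delivery row**

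16.54 − 10.58 = 5.96; SE = √((0.31² + 0.52²)/7) = 0.229; interval 5.46 to 6.46. The table prints 5.9 (5.4 to 6.4). All three entries look truncated, whereas the next row is rounded (6.57 appears as 6.6).

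**The case against.** The strongest reply is that this is a small matter that follows from a larger one. The percentages enter no test: the groups are compared by t-test at each visit, and time by ANOVA with Tukey comparisons. The abstract's results and conclusion are blank, and the document itself draws no comparison of percent gain between groups. A reader can also work out the change from the adjacent means. On Table 1's figures the discrepancy is 0.9 percentage points. All of that stands, and it limits the weight of the point.

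It can also be said that the percentage may not be the faulty number. A last-visit mean near 12.26 N would make 15.9% correct, and with two conflicting means in print neither is verified. That stands too. What is shown is that 15.9% fits neither printed mean, not which entry is in error. The digits match the absolute gain of 1.59 N, so newtons may have been entered as a percentage, but that is an inference.

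The same reasoning rules out a tempting stronger reading: that 15.9% overstates the 3D-printed denture's gain and so narrows the gap between groups. It does so only if 12.17 N is right. With 13.24 N it understates the gain, and Group I would have risen proportionally more than Group II.

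The Group II figure and the Table 2 delivery row are minor. The first is 0.13 points off; the second is a display issue of 0.06 N on a difference of about 6 N.

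**Conclusion.** The point holds in this form: the printed Group I increase of 15.9% cannot be obtained from either printed last-visit mean. It is 0.9 points above the 15.0% that follows from the text and Table 1, and 9.2 points below the 25.1% that follows from Table 2. Rounding, the other denominators tried and per-patient averaging do not close the first gap.

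The direction of the error, the replacement value and the ordering of the two groups on relative gain all depend on reconciling 12.17 with 13.24 N. A reader might infer that 15.0% is the correct value, or that every account of change over time is wrong. The documents support neither: the first assumes Table 1's mean is right, and the second overlooks the visit means, P values and Tukey letters. The percentage itself alters no test result.

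The conclusion assumes that the delivery mean of 10.58 N is right, that percent change runs from delivery to the last visit, and, for the per-patient bound, that Table 1's means and SDs apply with n = 7.

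**What to change.** In this order:

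1. Reconcile the Group I last-visit means of 12.17 and 13.24 N against the source readings, and correct whichever table and text are wrong.
2. Recompute both percent changes from those readings. State the formula: change in mean over delivery mean, or mean of per-patient percentages.
3. Print the absolute gain in newtons beside each percentage, in the text and in Table 1. By the change-in-means formula, Group I is 1.59 N (15.0%) if 12.17 N is confirmed, or 2.66 N (25.1%) if 13.24 N is. Group II is 3.33 N (20.1%).
4. As a minor correction, round the Table 2 delivery row instead of truncating it: 5.96 N, 95% CI 5.46 to 6.46.

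The cost is a recalculation from data already held. No new measurements are needed. If the reconciliation confirms 13.24 N, the Tukey letters for Group I in Table 1 need rechecking as well.
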